4.4.2 Day

Start Date and End Date fields in the listings have a Day associated with them. Day = 1 will be determined by the date/time of when the first split dose of the test article is consumed. Days prior to this will be negative.

In the tables and listings when referring to a specific Visit, e.g., Day 0, Day 1, ..., Day 14, refer to Visit names given in Appendix 1 Schedule of Assessments in the study protocol.

4.4.3 Definition of Baseline Values

Unless otherwise specified, Baseline values are defined as the last values collected before the first split dose of test article.

4.4.4 Windowing of Visits

All data will be categorized based on the scheduled visit at which it was collected. These visit designators are pre-defined values indicated in the Schedule of Assessments (Appendix 1 of the protocol).

4.4.5 Justification of Pooling

Due to the expected low enrollment of subjects at each site, and the multitude of selected sites, data from all sites will be pooled. Study center or treatment-by-center interaction terms will not be included in statistical analyses.

4.5 Output Production and Validation

All analyses will be performed using SAS V 9.3 or higher (SAS Institute, Inc., Cary, North Carolina, USA). Validation and quality control of the tables, listings, and figures which display the results of the statistical analysis of the data from this study, will follow the appropriate Innovative Analytics standard operating procedures (SOPs).

5 SUBJECT DISPOSITION

The number of subjects who are treated, complete the study, and reasons for discontinuation from the study will be summarized in tabular format for the safety population separately by subjects enrolled prior to 01Jan2022 and subjects enrolled after 01Jan2022. Subject disposition will also be displayed for the safety population in a subject listing.

6 DEMOGRAPHIC CHARACTERISTICS

Demographic and other characteristics will be summarized by treatment group and consist of (but will not be limited to) the following: age, sex, ethnicity, race, height, weight, and BMI.

For quantitative variables, summary statistics (n, mean, SD, minimum, first quartile, median, third quartile, and maximum) will be presented for the safety population. For qualitative variables, results will be summarized as counts and percentages for the stratified safety population. Demographic and other characteristics will be tabulated also for the mITT population.

Individual demographic and other characteristics for the safety population will be displayed in subject listings. A variable indicating enrollment stratification will be included in the listing.

7 MEDICAL HISTORY

All medical history events will be coded using the Medical Dictionary for Regulatory Activities (MedDRA) coding system (Version 25.0). Medical history events (past and current medical disorders) will be presented by treatment group for the safety population, summarized by MedDRA System Organ Class (SOC) and Preferred Term.

Medical history events will be displayed for the safety population in a subject listing. Specific medical history will also be summarized and listed for the safety population.

8 SURGICAL PLANS AND ASSESSMENTS

A frequency table will be presented by treatment group for first and second surgical approach and the presence (absence) of a stoma. The table will be sub-divided by subjects enrolled prior to 01Jan2022 and subjects enrolled on or after 01Jan2022. All surgery information will be listed for the safety population.

9 PRIOR AND CONCOMITANT MEDICATIONS

All medications will be coded using the World Health Organization Drug Dictionary (WHO Drug) version March 2022. Frequency tables will be presented by treatment group for prior and concomitant medications taken during the study.

- Prior medications are defined as those taken with a start date prior to the first split dose of study medication and ongoing is No and a stop date prior to the date of the first split dose of study medication.
 - Medications with an unknown stop date will be considered concomitant
- Concomitant medications are defined as those with a start date on or after the first dose of study medication, or those with a start date before the first dose of study medication and a stop date on or after the first dose of study medication (including those medications which are classified as ongoing).

All prior and concomitant medications will be listed for the safety population. All concomitant treatments or procedures will be listed for the safety population.

10 DRUG EXPOSURE

The number and percent of subjects who consumed all of one or both doses will be presented by treatment group for the safety population. The estimated volume of each dose received will be summarized by treatment group. Subject satisfaction with the taste will also be presented by treatment group for the safety population. Additionally, subject satisfaction will be further classified by those who completed both doses and those who did not within treatment group. All findings will be displayed in subject listings. A symmetric scatter plot matrix will be used to display via histograms and scatter plots the relationship between Time to GI2, Change in Adhesion Score, and Time from last dose to start of surgery. There will be one cell in a plot matrix for each stratum surgery type (laparoscopic, minimally invasive) and for each of the test articles (LB1148, placebo).

11 EFFICACY ANALYSIS

11.1 Primary Endpoints

11.1.1 Intra-Abdominal Adhesions

The primary efficacy endpoint for this study involves intra-abdominal adhesions and is as follows:

- Extent and severity of intra-abdominal adhesions as determined by the surgeon using the Intra-Abdominal Adhesion Extent and Severity Assessment Worksheet (Appendix 5 of the protocol)

If successful, this proof-of-concept study should provide necessary statistical information that when combined with information on clinical significance will allow for the computation of meaningful effect size and power calculations to support a subsequent phase 3 study(ies) with the following hypotheses: The null hypothesis for these primary efficacy endpoints is that there is no significant difference in intra-abdominal adhesions (extent and severity) between treatment groups; the alternative hypothesis is that there is a significant reduction in intra-abdominal adhesions (extent and severity) between treatment groups.

The presence or absence of adhesions, surgeon-recorded values for the extent and severity of visible intra-abdominal adhesions using the Intra-Abdominal Adhesion Extent and Severity (Appendix 5 of the protocol) will be recorded at both the first and second surgeries. The following nine variables will be calculated at both the first and second surgeries and summarized:

1. Summed Bowel-to-Abdominal Wall Adhesions Extent Score = bowel-to-abdominal wall extent scores summed across all 9 quadrants
2. Summed Bowel-to-Abdominal Wall Adhesions Severity Score = bowel-to-abdominal wall severity scores summed across all 9 quadrants
3. Bowel-to-Abdominal Wall Summed Extent and Severity Scores = add the Bowel-to-Abdominal Wall extent and severity scores together
4. Summed Bowel-to-Bowel Adhesions Extent Score = bowel-to-bowel extent scores summed across all 9 quadrants
5. Summed Bowel-to-Bowel Adhesions Severity Score = bowel-to-bowel severity scores summed across all 9 quadrants
6. Bowel-to-Bowel Summed Extent and Severity Scores = add the Bowel-to-Bowel extent and severity scores together
7. Bowel-to-Abdominal Wall and Bowel-to-Bowel Summed Extent and Severity Scores = add the Bowel-to-Abdominal Wall Summed Extent and Severity Scores (i.e., [3] above) to the Bowel-to-Bowel Summed Extent and Severity Scores (i.e., [6] above)
8. Take the Maximum of the Bowel-to-Bowel Severity Scores over all 9 regions
9. Bowel to Abdominal Wall Summed Severity Score added to the maximum Bowel to Bowel Severity Scores over the 9 regions, i.e., [2] and [8] are summed to obtain the Cocclini Peritoneal Adhesion Index (PAI)

Descriptive statistics as detailed in Section 4.2 as well as 95% confidence intervals will be provided for the nine extent and severity score detailed above across treatment groups and stratified by surgery type.

The summed extent and severity scores specified above (only # 7) will be compared between treatment groups at both the first and second surgeries, using a van Elteren test which allows for

the incorporation of the stratification factor type of surgery (laparotomy versus minimally invasive approaches) into the analysis. Additionally, the change from baseline in the summed extent and severity scores (i.e., from the first surgery to the second surgery) will be compared between treatment groups using a van Elteren test, again allowing control for surgery type. (This comparison will also be performed for that subgroup of subjects who had adhesions observed at the time of the first surgery.)

As stated in Section 4.2, all p-values obtained will be considered nominal.

All results will be summarized by treatment group for the mITT and PP populations. All findings will be presented in subject listings for the mITT population.

11.2 Secondary Endpoints

11.2.1 Intra-Abdominal Adhesions

The secondary efficacy endpoints for this study involve intra-abdominal adhesions and are as follows:

- Incidence of intra-abdominal adhesions at the second surgery
Intra-abdominal lesions (Y/N) will be compared between treatment groups (LB1148 or Placebo) at both the first and second surgeries, analyzed using counts and percentages with comparisons made using the Cochran-Mantel-Haenszel (CMH) to obtain 95% Wald Confidence limits for the relative risk of adhesions along with the chi-square test, which allows for the incorporation of the stratification factor type of surgery (laparotomy versus minimally invasive approaches) into the analysis chi-square test for homogeneity of proportions. The change in proportion between the two surgeries will be evaluated across treatment and stratified by surgery type.
- Extent and severity of adhesions at the second surgery (Incorporated into the tables leading to the primary endpoint)
- Change from baseline in the incidence of intra-abdominal adhesions (Simple shift table)
- Compare change from baseline in incidence, extent, and severity of intra-abdominal adhesions among subjects treated with LB1148 or placebo who had adhesions observed at the time of the first surgery. (A subset of the primary endpoint analysis.)
- Compare number of adhesions between the LB1148 and placebo groups
- Compare change between the two surgeries in the number of adhesions between the LB1148 and placebo groups

11.2.2 Bowel Function Endpoints

The secondary efficacy endpoints include the number of hours from surgical closure to resolution or presence, as appropriate, of:

- Achievement of GI2, defined as the toleration of solid food (subject finished a meal that required chewing and experienced no significant nausea/vomiting for four hours) and the

recovery of the upper and lower GI tract (first bowel movement; passage of stool) following surgery (the time the last skin staple or suture was placed by the surgeon)

- Nausea with a Verbal Rating Score (VRS) ≥ 3 (moderate to severe) (Listing only)
- Vomiting or retching* (Listing only)
- Presence of flatus (Listing only)
- Bowel movement (presence of stool from anus or ostomy)
- Insertion and reinsertion of nasogastric (NG)/orogastric (OG) tube*
 - Removal of NG/OG tube* (Listing only)
- Ability to tolerate a liquid oral diet (liquid diet ordered, and subject is able to sustain oral liquid intake without need for IV fluid administration for hydration)
- Ability to tolerate a solid oral diet (solid food ingestion without significant nausea/vomiting for four hours)
- Achievement of GI3, identical to GI2 except recovery of the upper and lower GI tract is defined by either bowel movement or flatus
- Resolution of POI, defined as having resolved when all of the following criteria are met:
 - Absence of nausea AND vomiting for 12 hours without a NG/OG tube
 - Ability to tolerate a solid or liquid oral diet
 - Passage of flatus OR stool over the preceding 24 hours

The following POI parameters will also be evaluated:

- Incidence of POI (Within 14 days of first surgery, After Discharge), defined as the greater than expected inability to tolerate liquids or solids during the post-operative period
 - Within 14 days of first surgery subjects will be identified by AE preferred term (PT) **and** by a confirmatory imaging study within the start/stop dates of the POI
 - The AE PTs are ileus, post-operative ileus, small bowel obstruction, bowel obstruction, partial bowel obstruction, mechanical bowel obstruction, and non-mechanical bowel obstruction
- Incidence of POI after hospital discharge
 - Subjects will be identified by AE PT as listed above

*Vomiting and retching, as well as insertion, reinsertion, and removal of NG/OG tube will be treated as binary (yes/no) variables.

Selected time-to-event secondary efficacy endpoints (See Table in Section 11.5) will be analyzed using a stratified Cox PH model with treatment as the main effect, stratified by surgery type (laparotomy versus minimally invasive). In addition to surgery type, a categorical age (<65 years, ≥ 65 years) will be included. Nominal p-values will be reported. Comparison of treatment groups and assessment of the significance of the parameter estimates for surgery type will be made using the Wald chi-square test.

In addition to the semi-parametric Cox PH model, non-parametric Kaplan-Meier survival curves will be produced for the two treatment groups and compared using a stratified log-rank test; results from this test will be considered nominal/hypothesis-generating in nature. The number of hours to each endpoint will be presented in summary tables with descriptive statistics for the mITT (all variables selected) and PP populations (POI, GI2, and GI3 variables only).

Those endpoints defined as yes/no variables will be analyzed using a chi-square test for homogeneity of proportions.

All findings will be presented in subject listings for the mITT population, including calculated time to event efficacy variables.

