2.3.2. Safety Endpoints

Safety and tolerability will be assessed based on the incidence and severity of treatment emergent adverse events (AEs), serious adverse events (SAEs), vital signs, clinical laboratory results.

Specific safety sub-analyses will be performed to assess the safety of LB1148 in the following patient populations:

[figure not shown]
- patients who are on chemotherapy;
- patients with a venous port or catheter;
- patients with varicose veins and superficial vein thrombosis;
- patients with varying degrees of obesity;
- patients who are smokers;
- patients with varying degrees of renal function; and
- patient age groups, including 65-80 years old.

INVESTIGATIONAL PLAN

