7.5. Post-Operative Ileus

Resolution of POI-related symptoms are one of the focuses of this study. As such, any instance of POI will be recorded as an AE/SAE and followed to resolution. POI events post-discharge, but prior to Day 30, will also be recorded as an AE/SAE.

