¹³ Phone call for follow-up to gather any hospital readmission and vital status after initial hospital discharge information. Only readmissions (SAEs) should be recorded and reported.

¹⁴ Only AE/SAEs related to the surgical procedure will be recorded and reported.

¹⁵ Refer to [Error! Reference source not found.](#) for a list of Laboratory Tests. Labs are collected on Screening and Post-Operative Day 3. Post-Operative Day 7 labs will only need to be performed only if subject is still hospitalized.

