11.5 Efficacy Time-to-Event Parameter by Analysis Type

Number of hours to Analysis	Cox PH		Kaplan-Meier		Other	
	mITT	PP	mITT	PP	mITT	PP
GI2	Yes	Yes	Yes	Yes	Frequency Table	Frequency Table
Bowel movement within 14 days	Yes	No	Yes	No	Frequency Table	No
NG/OG use (insertion, reinsertion)	No	No	No	No	Frequency Table only	No
NG/OG removal	No	No	No	No	Listing only	No
Liquid oral diet	No	No	Yes	No	Frequency Table	No
Solid oral diet	Yes	No	Yes	No	Frequency Table	No
GI3	Yes	Yes	Yes	Yes	Frequency Table	Frequency Table
POI within 14 days	Yes	Yes	Yes	Yes	Frequency Table	Frequency Table

Number of hours to Analysis	Cox PH		Kaplan-Meier		Other	
POI after discharge	No	No	No	No	Included in Frequency Table for POI within 14 days	No
Discharge order written	Yes	Yes	Yes	Yes	No separate descriptive Frequency Table	No separate descriptive Frequency Table
Actual discharge	Yes	Yes	Yes	Yes	No separate descriptive Frequency Table	No separate descriptive Frequency Table
Standard discharge	No	No	No	No	Listing only	No
Nausea	No	No	No	No	Listing only	No
Vomiting	No	No	No	No	Listing only	No
Flatus	No	No	No	No	Listing only	No

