12 SAFETY ANALYSIS

12.1 Adverse Events

All adverse events will be coded using the Medical Dictionary for Regulatory Activities (MedDRA) coding system (Version 25.0). Frequency tables will be presented by treatment group for all adverse events (AEs) by system organ class and preferred term for the safety population. Frequency tables will also be presented for AEs leading to discontinuation of test article, AEs by maximum severity (per CTCAE Version 5.0 Section 7.11 Study Protocol), AEs related to test article, and serious AEs. Subject listings of all AEs will also be provided for the safety population.

In all displays, adverse events will be displayed by MedDRA System Organ Class (SOC) and Preferred Terms. Subjects who have the same AE occur more than once will be counted only once for that event. Subjects who have more than one AE within a system organ class will be counted only once in that system organ class. (The addition of severity or relatedness follow the same pattern.)

In addition, frequency tables by treatment group for all AEs by system organ class and preferred term will be presented for the following populations:

- Patients who have had chemotherapy in the last 60 days
- Patients with a venous port or catheter
- Patients with varicose veins and superficial vein thrombosis
- Patients with varying degrees of obesity
 - Baseline BMI 30-35
 - Baseline BMI 35-40
- Patients who are smokers
- Patients with varying degrees of renal function

- Baseline eGFR 45-59
- Baseline eGFR 30-44
- Baseline eGFR 15-29
- Baseline eGFR < 15
- Patient age groups
 - 18-64 years
 - 65-80 years

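### The SAP's post-discharge POI count has no end date and its AE tables have no split at the second surgery, so takedown events would be mixed with first-surgery events

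*SAP*

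**What the plan says.** **POI incidence.** SAP 11.2.2 has two items. The first is tied to an operation and a window, "Within 14 days of first surgery subjects will be identified by AE preferred term (PT"), and also needs a confirmatory imaging study dated within the event. The second, POI after hospital discharge, has one rule: "Subjects will be identified by AE PT as listed above". The list it refers to is broad: "The AE PTs are ileus, post-operative ileus, small bowel obstruction, bowel obstruction, partial bowel obstruction, mechanical bowel obstruction, and non-mechanical bowel obstruction". In SAP 11.5 the mITT entry for POI after discharge reads "Included in Frequency Table for POI within 14 days". There is no per-protocol, Cox or Kaplan-Meier analysis of it.

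**The protocol's limit.** Protocol 7.5 states: "POI events post-discharge, but prior to Day 30, will also be recorded as an AE/SAE". Protocol 2.3 makes imaging confirmation part of the definition of POI itself.

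**What is collected later.** Under protocol Section 7, routine AE collection runs from first dose to the earliest of Day 14, discharge or termination. Readmissions are then recorded as SAEs through the second surgery visit (Section 7 opening and 6.16) or the Month 3 visit (7.9). AEs of the second surgery are also collected. Appendix 1, footnote 14, restricts these: "Only AE/SAEs related to the surgical procedure will be recorded and reported".

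**AE tables.** SAP 12.1 says: "Frequency tables will be presented by treatment group for all adverse events (AEs) by system organ class and preferred term". The tables use the safety population, count a subject once per term, and include one by maximum severity. The protocol's safety endpoint (2.3.2) is "incidence and severity of treatment emergent adverse events (AEs"). The SAP does not say when that period ends.

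**The concern.** Study drug is given only in the hours before the first operation. The second operation, usually a stoma takedown, may come up to 8 months after enrollment, or later with Medical Monitor approval. It is itself abdominal surgery that can be followed by ileus, obstruction and other complications. If those events are in the database and the SAP's counting rules have no end date, two things follow.

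- The post-discharge POI row, shown in the same table as POI in the 14 days after the first surgery, would also contain ileus from a different operation.
- The AE tables would merge two operations. A subject with Grade 1 ileus after the first surgery and Grade 3 ileus after takedown appears once, at Grade 3.

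This matters because protocol 7.3 names POI, thrombotic events and prolonged hospitalization from a post-surgical complication as the events of special interest, and each can arise from either operation.

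**Working it through.** The plan states no rate, power or sample size for POI or AEs, so there is no figure to reproduce. The main check is a comparison of rules.

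**1. Is there an end date in the SAP?** The 14-day item has one. The post-discharge item does not. Its parent bullet refers to the post-operative period without saying of which surgery. By contrast, SAP 3.3 limits all four exploratory objectives to the first surgery, including bowel obstruction through 30 days, and obstruction terms are in the POI list. The missing limit on POI therefore looks unintended.

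**2. Are later events in the database?** Yes. Readmissions are recorded past Day 30 whether the Section 7 opening or 7.9 applies, and procedure-related AEs of the second surgery are recorded. A readmission for obstruction at Month 4, or ileus after takedown, would meet the SAP rule if coded to a listed term.

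**3. Which population is affected?**
- POI row: mITT only (SAP 11.5), so only subjects dosed on or after 01Jan2022 (SAP 4.1).
- AE tables: safety population, which also holds the pre-2022 subjects, for whom the second surgery was optional (SAP 4.1 and 14). SAP 5 and 8 split their tables at that date; 12.1 does not.

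**4. Do the two POI rows overlap?** Yes. Take discharge on Day 5 and ileus on Day 9. The event is after discharge, with no imaging needed, and also within 14 days, but there only with imaging.

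**5. Scale, under assumed rates.** Let q be the ileus risk after takedown, equal in both arms, and p the risk of post-discharge POI to Day 30. Neither is in the documents.

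*Expected takedown cases.* SAP 4.3 expects at least 30 randomized from up to 40 enrolled. If all reach takedown, the count is N × q: 30 × 5% = 1.5 up to 40 × 20% = 8. If half do, it is 15 × 5% = 0.75 up to 20 × 20% = 4.

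*Share of cases from takedown,* q/(q + p): 5/(5 + 5) = 50%; 10/(10 + 5) = 67%; 20/(20 + 3) = 87%. The result depends on the assumed ratio of q to p.

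*Effect on a comparison.* The risk of ever having an event under the open window is 1 − (1 − p)(1 − q). With p = 10% on placebo and 5% on LB1148:

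| q | Placebo | LB1148 | Relative risk |
|---|---|---|---|
| 0 (Day-30 limit) | 0.100 | 0.050 | 0.50 |
| 5% | 1 − 0.90 × 0.95 = 0.145 | 1 − 0.95 × 0.95 = 0.098 | 0.67 |
| 10% | 0.190 | 0.145 | 0.76 |
| 15% | 0.235 | 0.193 | 0.82 |
| 20% | 0.280 | 0.240 | 0.86 |

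If q differed between arms, the relative risk could move either way.

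**The case against.** The strongest reply is that the context already narrows the rule. Hospital Discharge is a single visit after the first resection, Second Surgery is a separate study period (SAP 2), data are categorized by scheduled visit (SAP 4.4.4), and listings carry study days (SAP 4.4.2). Protocol 7.5 limits the recording of post-discharge POI. A careful programmer might apply Day 30 unprompted. This shows that late events could be identified. It does not supply a rule for the summary tables, and 11.2.2 applied as written includes the late events.

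The stakes are also modest. The row is secondary, has no time-to-event analysis, and all p-values are nominal (SAP 4.2). That stands.

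Several stronger readings are tempting but unsupported:

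- *Takedown events would dominate the row.* This needs ileus rates, which the documents do not give.
- *Pre-2022 subjects distort the POI row.* They are not in the mITT population; the point applies only to the safety tables.
- *Without a treatment-emergent definition, pre-dose events enter the tables.* AE collection starts at first dose, apart from events suspected to be caused by a protocol procedure (protocol 7.9). Essentially only the end of the window is open.
- *The overlapping rows double count.* SAP 11.5 specifies no combined total, so this happens only if the rows are added.
- *Takedown events say nothing about the drug.* The trial's target is adhesions, and protocol 1.3 links adhesions to obstruction and harder later surgery. Such events may be informative, which is a reason to show them separately and not to discard them.

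**Conclusion.** The point holds as a gap in the counting rules. SAP 11.2.2 does not carry over the Day-30 limit of protocol 7.5 and does not exclude the second surgery, and SAP 12.1 has no split at the second surgery. Applied literally, these rules put takedown ileus or obstruction into the mITT post-discharge POI row and merge two operations in the safety tables. In the safety tables alone, subjects with an optional second surgery are also pooled with subjects for whom it is required, so their opportunity for second-surgery AEs differs.

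The size is unknown. The figures in the working rest on assumed rates, and the relative-risk illustration also on equal takedown risk in the two arms and every subject having the second surgery. They show that the mixing could be material, not that it will be. The primary endpoint is unaffected. The change is worth making because it is cheap and removes an avoidable ambiguity about which operation an event belongs to.

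**What to change.** **SAP 11.2.2.** Define POI after discharge as onset after first-surgery discharge, before Day 30 (protocol 7.5) and before any second surgery. State which day numbering applies, since protocol Day 0 is the day of surgery while SAP 4.4.2 sets Day 1 at the first split dose. State how an event that is both after discharge and within 14 days is assigned. Reconcile the imaging requirement, now applied to only one of the two rows, with the protocol's definition of POI.

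**SAP 12.1.** Keep the overall AE table and add tables by onset date for three periods: first dose to Day 30, interval readmissions, and second-surgery events. Give ileus or obstruction after the second surgery its own row.

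**Cost.** SAP wording and one period flag derived from AE start dates and surgery dates already collected. The downside is a few more tables.

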4 GENERAL METHODS

4.1 Analysis Populations

Due to coronavirus disease 2019 (COVID-19), some subjects enrolled and randomized prior to 01Jan2022 were released from the hospital prior to achieving GI2. In addition, subjects were randomized based on whether the surgery was to include a stoma or not and a subject was considered completed at Study Day 30, e.g., the second surgery was optional. Protocol Amendment 5 and 6 require subjects to have a stoma during the first surgery and require the second surgery for the subjects to be considered complete. The primary endpoint is now comparing the change from baseline in extent and severity of intra-abdominal adhesions rather than GI2 among subjects treated with LB1148 or placebo. These circumstances and changes require corresponding updates to the populations defined in the Study Protocol.

The **modified Intent-to-Treat (mITT)** population includes all randomized subjects who received any investigational test article on or after 01Jan2022, where subjects will be analyzed according to the treatment to which they were randomized.

Safety Population: The safety population will be defined as all subjects who receive any amount of investigational test article. Subjects will be analyzed according to the treatment actually received.

The **Per Protocol Population (PP)** includes subjects in the mITT population who met all inclusion and no exclusion criteria, received the complete appropriate study dose, and had no important protocol deviations or violations, where subjects will be analyzed according to the treatment to which they were randomized.

Study subjects may be replaced if found to be ineligible (violation of one or more inclusion/exclusion criteria), or if following randomization, did not go on to receive ANY amount of investigational test article.

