4.2 Summarization of Data

Study results will be summarized in tabular format by treatment group, with descriptive statistics and/or in subject listings. In general, descriptive statistics for continuous variables will consist of subject count (n), mean, standard deviation (SD), minimum, first quartile, median, third quartile and maximum. Descriptive statistics for categorical variables will consist of subject counts and percentages.

All available safety and efficacy data will be included in data listings.

The efficacy analyses described in this Statistical Analysis Plan will be performed for the mITT (all efficacy endpoints) and PP Populations (primary efficacy endpoint and selected secondary efficacy endpoints), while the safety analyses will be performed for the Safety Population. All statistical tests will be 2-sided, with p-values considered nominal for this proof-of-concept study, although a p-value <0.05 will be highlighted. Unless otherwise specified, p-values will be reported to four (4) digits. No multiplicity adjustments will be performed.

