4.3 Sample Size Justification and Randomization

This proof-of-concept study was originally designed to utilize an adaptive sample size re-estimation to allow for sample size adjustment based on observed data from the interim analysis. No formal knowledge of the effect size is given; therefore, no power calculations were used to assess type I and type II error rates. The goal of this study is to assess the observed effect size at the interim and adjust sample size accordingly.

Initially, subjects were randomized into an active or placebo group following a 1:1 ratio while stratified for surgery type (laparotomy or minimally invasive) and stoma (planned or unplanned). After the first 50-60 subjects were enrolled, an interim analysis was planned to assess GI2 and LOS (Discharge Order Written) endpoints. If the treatment effect size, conditional power, or reproducibility probability was deemed insufficient at the interim, then the sample size would be increased accordingly, from 120 up to 200 subjects.

The sample size justification as originally designed no longer applies to the new primary endpoint (change from baseline in extent and severity of intra-abdominal adhesions among subjects treated with LB1148 or placebo). Enrolling up to 40 subjects is estimated to provide at least 30 randomized subjects, which should be adequate to explore the feasibility of the new endpoint. The data collected from the subjects in this study will be available to power a future study using this endpoint.

Subjects randomized after 01Jan2022 were randomized by surgery type but within the planned stoma arm only.

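### The yes/no bowel-function endpoints get a chi-square with no stratification by surgery type and no between-arm estimate, unlike the SAP's other binary comparisons

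*SAP*

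**What the plan says.** SAP 11.2.2 gives one sentence on the binary bowel endpoints: "Those endpoints defined as yes/no variables will be analyzed using a chi-square test for homogeneity of proportions". The footnote to the endpoint list says that vomiting and retching, and tube insertion, reinsertion and removal, "will be treated as binary (yes/no) variables". POI incidence is binary by nature but is not in that footnote.

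The table in SAP 11.5 narrows the reach. Vomiting and tube removal are restricted to listings. Tube insertion or reinsertion is limited to a frequency table, with no Cox or Kaplan-Meier analysis. POI within 14 days has Cox, Kaplan-Meier and a frequency table. POI after discharge has no model and is only counted in that frequency table.

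On design, SAP 4.3 says "Subjects randomized after 01Jan2022 were randomized by surgery type but within the planned stoma arm only" and "Enrolling up to 40 subjects is estimated to provide at least 30 randomized subjects". SAP 4.1 limits the efficacy set to subjects dosed on or after that date. SAP 4.2 adds: "All statistical tests will be 2-sided, with p-values considered nominal for this proof-of-concept study, although a p-value <0.05 will be highlighted".

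Elsewhere the SAP brings surgery type into its binary comparisons. Section 11.2.1 analyzes adhesion incidence with CMH and 95% limits for the relative risk, "which allows for the incorporation of the stratification factor type of surgery (laparotomy versus minimally invasive approaches)". Section 11.3 uses CMH with confidence intervals for exploratory categorical endpoints.

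**The concern.** Two things are missing from the sentence in 11.2.2.

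The first is the stratification factor. When allocation is balanced within strata and the event rate differs between them, a pooled chi-square uses a variance that includes the between-stratum spread. That spread cannot contribute to the treatment difference, so the test rejects too rarely.

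The second is an estimate. The study's declared use is to inform later trials. At 30 to 40 subjects with nominal p-values, a difference or ratio with its interval is the more useful output. As written, a secondary binary endpoint gets less than an exploratory categorical one, and the SAP gives no reason.

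**Working it through.** **Inputs from the documents.** 1:1 allocation, 30 to 40 subjects (15 to 20 per arm), stratification by surgery type, two-sided 0.05. The documents give no power, effect size or event rate for these endpoints, so there is no figure of the plan's own to reproduce.

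**Assumptions.** Event rates by surgery type, and the split of subjects between strata.

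**Large-sample formula.** Size of the unstratified test = 2 × [1 − Φ(1.96/√r)], where r = mean within-stratum variance ÷ pooled variance.

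For 10 + 5 per arm and rates 0.10/0.40:
- pooled rate = (2/3)(0.10) + (1/3)(0.40) = 0.20; pooled variance = 0.20 × 0.80 = 0.16
- within-stratum variance = (2/3)(0.09) + (1/3)(0.24) = 0.14
- r = 0.14/0.16 = 0.875; size = 2 × [1 − Φ(2.095)] = 0.036

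**Exact size.** Full enumeration of two strata by two binomial arms, Pearson chi-square against CMH without continuity correction:

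| Per arm, by stratum | Rates by stratum | Chi-square | CMH |
|---|---|---|---|
| 10 + 5 | 0.20/0.20 | 0.050 | 0.045 |
| 10 + 5 | 0.10/0.20 | 0.035 | 0.039 |
| 10 + 5 | 0.10/0.30 | 0.038 | 0.046 |
| 10 + 5 | 0.10/0.40 | 0.036 | 0.048 |
| 10 + 5 | 0.10/0.60 | 0.024 | 0.048 |
| 10 + 10 | 0.20/0.20 | 0.050 | 0.050 |
| 10 + 10 | 0.10/0.20 | 0.047 | 0.048 |
| 10 + 10 | 0.10/0.30 | 0.043 | 0.047 |
| 10 + 10 | 0.10/0.40 | 0.038 | 0.048 |

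**Exact power, chi-square against CMH.**
- 10 + 5, placebo 0.20/0.60, LB1148 0.02/0.20: 40.9% against 45.0%
- 10 + 10, placebo 0.20/0.60, odds ratio 0.25: 38.2% against 41.9%
- 10 + 10, placebo 0.30/0.50, odds ratio 0.25: 44.6% against 44.5%
- 8 + 7, placebo 0.30/0.50, odds ratio 0.25: 35.2% against 33.3%

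**Sparse tables.** With equal arms, the smallest expected count in the pooled table is half the number of subjects with the rarer outcome. At 15 per arm it is below 5 in 99.95% of trials at a common event rate of 10%, 99.0% at 15%, 93.9% at 20%, 59% at 30% and 18% at 40%.

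**Planned estimates, row by row (SAP 11.5).** POI within 14 days: a hazard ratio is obtainable from the stratified Cox model. POI after discharge and NG/OG use: counts and percentages by arm only, with no difference, ratio or interval.

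**The case against.** The strongest reply is that little rests on this sentence. All p-values are nominal, nothing is powered, and the endpoint closest to the study's purpose, POI within 14 days, already has stratified Cox and Kaplan-Meier analyses in both the mITT and PP populations. Percentages by arm are tabulated, so a reader can form a crude difference. The wording may also be shorthand: 11.2.1 attaches the same phrase about homogeneity of proportions to a stratified CMH description. All of this stands and keeps the point modest. It does not supply an estimate for the two rows without one, and a programmer could still read the sentence either way.

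Four stronger readings are tempting and go too far:

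- **That the p-values are too conservative.** The documents give no event rates by surgery type, and the clear losses need assumed gaps of 30 points or more.
- **That every other efficacy test uses surgery type.** The two adhesion-number comparisons in SAP 11.2.1 name no test, and Protocol 9.3.1 plans an unstratified Wilcoxon test for the primary endpoint.
- **That these endpoints yield only a p-value.** This ignores the tabulated percentages and the Cox model for POI within 14 days.
- **That vomiting is affected.** It is restricted to a listing.

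**Conclusion.** The point holds as an inconsistency and a missing estimate. It is not a demonstrated bias. The sentence omits the factor used in randomization and gives no between-arm estimate or interval, while the SAP's other binary comparisons have both. Its practical reach is POI incidence, plus NG/OG insertion or reinsertion if that is tested at all, which 11.5 leaves unclear.

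The effect on the test depends on the assumed rates. At 15 per arm split 10 + 5, the loss in size is about 0.012 for a 30-point gap between surgery types (0.048 − 0.036) and about 0.008 for a 20-point gap (0.046 − 0.038). With equal rates there is no loss from omitting the stratum. The power gain from CMH reaches about 4 points at most in the scenarios run, and CMH is slightly worse in some. The stronger reason to change is the estimate, because POI after discharge and NG/OG use currently have none.

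**What to change.** Replace the sentence in SAP 11.2.2 with: *Yes/no endpoints will be compared with a CMH test stratified by surgery type, as in Section 11.2.1, with the stratified relative risk or risk difference and its 95% CI.* Name POI incidence explicitly as one of these endpoints. State whether NG/OG insertion or reinsertion is tested, and make the entry in 11.5 agree.

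Of the two measures, the risk difference can still be estimated when one arm has no events. That is a realistic case: at an assumed 10% rate and 15 subjects, its probability is 0.9^15 = 0.21.

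Do not add a mid-P exact rule triggered by expected counts below 5. In a stratum with 5 per arm, the smallest expected count is at most 2.5, so on within-stratum counts the rule would always apply. It is also more conservative than CMH: at 10 + 5 with rates 0.10/0.40 its size is 0.031, and in the first power example its power is 38.2%, below both the chi-square (40.9%) and CMH (45.0%).

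The cost is SAP wording and minor programming. CMH is already specified in 11.2.1 and 11.3, and no additional data are needed.
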